8. ETHICAL AND REGULATORY REQUIREMENTS

8.1 Ethical conduct of the study

The study will be performed in accordance with ethical principles that have their origin in the Declaration of Helsinki and are consistent with International Conference on Harmonisation

(ICH)/Good Clinical Practice (GCP), applicable regulatory requirements and the AstraZeneca policy on Bioethics and Human Biological Samples.

8.2 Subject data protection

The ICF will incorporate (or, in some cases, be accompanied by a separate document incorporating) wording that complies with relevant data protection and privacy legislation.

AstraZeneca will not provide individual genotype results to volunteers, any insurance company, any employer, their family members, general physician any other third party, unless required to do so by law.

Extra precautions are taken to preserve confidentiality and prevent genetic data being linked to the identity of the volunteer. In exceptional circumstances, however, certain individuals might see both see both the genetic data and the personal identifiers of a volunteer. For example, in the case of a medical emergency, an AstraZeneca Physician or the Principal Investigator might know a volunteer's identity and also have access to his or her own genetic data. Also Regulatory authorities may require access to the relevant files, though the volunteer's medical information and the genetic files would remain physically separate.

8.3 Ethics and regulatory review

Approval to administer the chosen dose of radioactivity will be sought from the Department of health (United Kingdom) Administration of Radioactive Substances Advisory Committee (ARSAC) prior to commencing the study. As part of the CSP review process, the CSP will be reviewed and approved by the ARSAC certificate holder.

An Ethics Committee (EC) should approve the final CSP, including the final version of the ICF and any other written information and/or materials to be provided to the volunteers. The Principal Investigator will ensure the distribution of these documents to the applicable EC, and to the study centre staff.

The opinion of the EC should be given in writing. The Principal Investigator should submit the written approval to AstraZeneca before enrolment of any volunteer into the study.

The EC should approve all advertising used to recruit volunteers for the study.

AstraZeneca should approve any modifications to the ICF that are needed to meet local requirements.

If required by local regulations, the CSP should be re-approved by the EC annually.

Before enrolment of any volunteer into the study, the final CSP, including the final version of the ICF, is approved by the national regulatory authority or a notification to the national regulatory authority is done, according to local regulations.

AstraZeneca will handle the distribution of any of these documents to the national regulatory authorities.

AstraZeneca will provide Regulatory Authorities, ECs, and Principal Investigator with safety updates/reports according to local requirements, including suspected unexpected serious adverse reactions (SUSARs), where relevant.

The Principal Investigator is responsible for providing the EC and ARSAC certificate holder with reports of any serious and unexpected adverse drug reactions from any other study conducted with the investigational product. AstraZeneca will provide this information to the Principal Investigator so that he/she can meet these reporting requirements.

8.4 Informed consent

The Principal Investigator at the centre will:

- Ensure each volunteer is given full and adequate oral and written information about the nature, purpose, possible risk and benefit of the study.
- Ensure each volunteer is notified that they are free to discontinue from the study at any time.
- Ensure that each volunteer is given the opportunity to ask questions and allowed time to consider the information provided.
- Ensure each volunteer provides signed and dated informed consent before conducting any procedure specifically for the study. A separate ICF will be provided for genotyping.
- Ensure the original, signed ICF(s) is/are stored in the Investigator's Study File.
- Ensure a copy of the signed ICF is given to the volunteer.
- Ensure that any incentives for volunteers who participate in the study as well as any provisions for volunteers harmed as a consequence of study participation are described in the ICF that is approved by an EC.

8.5 Changes to the protocol and informed consent form

Study procedures will not be changed without the mutual agreement of the Principal Investigator and AstraZeneca.

If there are any substantial changes to the CSP, then these changes will be documented in a CSP amendment and where required in a new version of the CSP (Revised CSP).

The amendment is to be approved by the relevant EC, the ARSAC certificate holder, and if applicable, also the national regulatory authority, before implementation. Local requirements are to be followed for revised CSPs.

AstraZeneca will distribute any subsequent amendments and new versions of the CSP to the Principal Investigator. For distribution to the EC see Section 8.3.

If a protocol amendment requires a change to a study centre's ICF, AstraZeneca and the study centre's EC are to approve the revised ICF before the revised form is used.

If local regulations require, any administrative change will be communicated to or approved by the EC.

8.6 Audits and inspections

Authorised representatives of AstraZeneca, a regulatory authority, or an EC may perform audits or inspections at the centre, including source data verification. The purpose of an audit or inspection is to systematically and independently examine all study-related activities and documents, to determine whether these activities were conducted, and data were recorded, analysed, and accurately reported according to the CSP, GCP, guidelines of the ICH, and any applicable regulatory requirements. The Principal Investigator will contact AstraZeneca immediately if contacted by a regulatory agency about an inspection at the centre.

9. STUDY MANAGEMENT

9.1 Prestudy activities

Before the first volunteer is entered into the study, it is necessary for a representative of AstraZeneca to visit the investigational study site to:

- Determine the adequacy of the facilities
- Determine availability of appropriate volunteers for the study
- Discuss with the Principal Investigator (and other personnel involved with the study) their responsibilities with regard to protocol adherence, and the responsibilities of AstraZeneca or its representatives. This will be documented in a CSA between AstraZeneca and the Principal Investigator

9.2 Training of study site personnel

Before the first volunteer is entered into the study, an AstraZeneca representative will review and discuss the requirements of the CSP and related documents with the study centre staff and also train them in any study-specific procedures and system(s) utilised.

The Principal Investigator will ensure that appropriate training relevant to the study is given to all of these staff, and that any new information relevant to the performance of this study is forwarded to the staff involved.

The Principal Investigator will maintain a record of all individuals involved in the study (medical, nursing, and other staff).

9.3 Monitoring of the study

During the study, an AstraZeneca representative will have regular contacts with the study site, including visits to:

- Provide information and support to the Principal Investigator.
- Confirm that facilities remain acceptable.
- Confirm that the investigational team is adhering to the protocol, that data are being accurately and timely recorded in the CRFs, that biological samples are handled in accordance with the Laboratory Manual and that study drug accountability checks are being performed.
- Perform source data verification (a comparison of the data in the CRFs with the volunteer's medical records at the hospital or practice, and other records relevant to the study) including verification of informed consent of participating volunteers. This will require direct access to all original records for each volunteer (eg, study centre charts).
- Ensure withdrawal of informed consent to the use of the volunteer's biological samples is reported and biological samples are identified and disposed of/destroyed accordingly, and the action is documented, and reported to the volunteer.

The AstraZeneca representative will be available between visits if the Principal Investigator or other staff at the study centre needs information and advice about the study conduct.

Source data

Refer to the CSA for location of source data.

9.4 Study agreements

The Principal Investigator at the study centre should comply with all the terms, conditions, and obligations of the CSA, or equivalent, for this study. In the event of any inconsistency between this CSP and the CSA, the terms of CSP shall prevail with respect to the conduct of the study and the treatment of volunteers and in all other respects, not relating to study conduct or treatment of volunteers, the terms of the CSA shall prevail.

Agreements between AstraZeneca and the Principal Investigator should be in place before any study-related procedures can take place, or volunteers are enrolled.

9.4.1 Archiving of study documents

The Principal Investigator follows the principles outlined in the CSA.

9.5 Study timetable and end of study

The end of the study is defined as ‘the last visit of the last volunteer undergoing the study’.

The study is expected to start in Q2 2014 and to end by Q3 2014.

The study may be terminated at the study centre if the study procedures are not being performed according to GCP, or if recruitment is slow. AstraZeneca may also terminate the entire study prematurely if concerns for safety arise within this study or in any other study with AZD9291.

10. DATA MANAGEMENT

Data management will be performed by .

When the completed CRFs have been scanned and indexed, the data are entered into the study database and proofread.

The data collected through third party sources will be obtained and reconciled against study data.

Adverse events and medical/surgical history will be classified according to the terminology of the latest version of the Medical Dictionary for Regulatory Activities (MedDRA).

Medications will be classified according to the AstraZeneca Drug Dictionary. All coding will be performed by .

Data queries will be raised for inconsistent, impossible or missing data. All entries to the study database will be available in an audit trail.

The data will be validated as defined in the Data Management Plan. Quality control procedures will be applied to each stage of data handling to ensure that all data are reliable and have been processed correctly.

When all data have been coded, validated, signed, and locked, clean file will be declared. Any treatment revealing data may thereafter be added and the final database will be locked.

Data associated with biological samples will be transferred to laboratories internal or external to AstraZeneca.

Any genotype data generated in this study will be stored in the AstraZeneca genotyping LIMS database, or other appropriate secure system within AstraZeneca and/or third party contracted to work with AstraZeneca to analyse samples. The results from this genetic research may be reported in the CSR for the main study, or in a separate report as appropriate

11. EVALUATION AND CALCULATION OF VARIABLES

11.1 Calculation or derivation of safety variable(s)

11.1.1 Calculation of change from baseline

Change-from-baseline variables will be calculated for the safety variables listed below, as the post-treatment value minus the value at baseline. The baseline values will be as follows:

- Clinical laboratory tests: Day -1
- 12-Lead ECG:
 - Time-matched, Day -1 for time points through 24 hours postdose
 - Day 1 predose for all time points after 24 hours postdose
- Vital signs: Blood pressure and pulse rate
 - Time-matched, Day -1 for time points through 24 hours postdose
 - Day 1 predose for all time points after 24 hours postdose
- All other vital signs: Day 1 predose

If a volunteer is missing the baseline collection, the previous nonmissing evaluation will become the baseline value. If no baseline or previous-to-baseline evaluations exist, then the baseline value will be treated as missing and no change-from-baseline value will be calculated.

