3. STUDY PLAN AND PROCEDURES

3.1 Overall study design and flow chart

This will be a Phase I, open-label, single centre study to determine the rates and routes of absorption and elimination of a single dose of [^{14}C]-AZD9291 in healthy male volunteers, by assessment of concentrations of total [^{14}C] radioactivity in whole blood and plasma, AZD9291 (and metabolites AZ5104 and AZ7550) in plasma and urine, and percent recovery of radioactive dose in urine and faeces.

Healthy male volunteers, aged 30 to 65 years (inclusive), will be recruited at one study centre. It is expected that 8 volunteers will be sufficient to provide a reliable estimate of rates and routes of absorption and elimination and to ensure sufficient data.

Volunteers will be screened over a period of 28 days (prior to investigational product administration) for eligibility (Visit 1). Screening assessments include evaluation of clinical chemistry, haematology, urinalysis, a physical examination, vital signs, a full ophthalmological examination and 12-lead paper ECG. Study-related procedures will only be performed after signing of the informed consent form (ICF).

Eligible volunteers will be admitted to the study centre on Day -1 for assessment of AEs, clinical chemistry, haematology, urinalysis, ECG, and vital signs including weight (Visit 2) and will remain in the study centre for 21 days.

On the morning of Day 1 each volunteer will receive a single dose of 20 mg [^{14}C]-AZD9291 administered as an oral solution (free base equivalent) containing a nominal dose of 1 μCi (0.037 MBq) activity to determine the concentrations of total ^{14}C radioactivity, AZD9291 and metabolites (AZ5104 and AZ7550) in plasma and urine as well as measurements of total radioactivity of [^{14}C]-AZD9291 in blood, faeces and urine. Additionally [^{14}C]-AZD9291 metabolism in plasma, urine and faeces will be characterised, as appropriate.

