At any time the lactulose may be discontinued based on the judgement of the investigator (eg, if the subject experiences intolerable abdominal pains).

A study flow chart is shown in [Figure 1](#). The overall study plan and schedule of assessments are presented in [Table 2](#) and [Table 3](#).

Figure 1 Study flow chart

[figure not shown]

Table 2 Overall study plan

Assessment	Screening	Admission	Dosing day and sampling period		End of Study visit	
	1	2	Residential period	Weekly 24-hour residency	including poststudy physical examination	
Visit	1	2		3 through 5	6	
Days	-28 to -2	-1	1	2 to 21	(28 to 29, 35 to 36, 42 to 43) ^a	(84 to 85) ^b 24-hour residency
Informed consent	X					
Optional informed consent for genotyping ^c		X ^c				
Pharmacogenetic blood sample collection			X ^c			
Inclusion/exclusion	X	X				
Demography	X					
Height/weight/BMI ^d	X	X ^d			X ^d	
Medical/surgical history	X					
Prior/concomitant medication	X	X	X	X	X	
Physical examination	X				X	
Brief physical examination ^e		X	X			
Clinical chemistry, haematology ^f	X		X	X	X ^f	
Serology (hepatitis B surface antigen, hepatitis C antibody, and HIV)	X					
Estimate creatinine clearance ^g	X					
Ophthalmic examination	X ^h					
Urinalysis/urine microscopy ⁱ	X		X		X	

Table 2 Overall study plan

Assessment	Screening	Admission	Dosing day and sampling period		End of Study visit	
	1	2	Residential period	Weekly 24-hour residency	including poststudy physical examination	
Visit	1	2	1	2 to 21	3 through 5	6
Days	-28 to -2	-1	1	2 to 21	(28 to 29, 35 to 36, 42 to 43) ^a	(84 to 85) ^b 24-hour residency
Alcohol/urine drug screen/breath carbon monoxide test ^j	X	X				
Vital signs (supine blood pressure and pulse rate)	X		X ^k	X	X	X
12-Lead ECG ^l	X		X	X		X
Investigational product administration ^m			X			
PK blood/plasma collection ⁿ			X ⁿ	X ⁿ	X ⁿ	X
Urine collection ⁿ			X ⁿ	X ⁿ	X ⁿ	X ⁿ
Faeces collection ⁿ			X ⁿ	X ⁿ	X ⁿ	X ⁿ
Discharge				X		X ^o
Record AEs		X	X	X	X	X
Record SAEs ^p	X ^p	X ^p	X	X	X	X

AE: adverse event; BMI: body mass index; ECG: electrocardiogram; HIV: human immunodeficiency virus; PK: pharmacokinetics; SAE: serious adverse event.

a A visit window of ± 2 days could be applied from Day 28 onwards.

b Poststudy physical evaluations will be performed at the time of the last PK blood sample collection (Days 84 to 85) or at the point at which the volunteer discontinues from the study.

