6. COLLECTION OF STUDY VARIABLES

The study assessments are described in the sections below. The study plan and timing of these assessments are detailed in [Table 2](#) and [Table 3](#). Additional assessments may be performed if the Principal Investigator considers them necessary for volunteer safety.

It is important that PK sampling occurs as close as possible to the scheduled time. In order to achieve this, other assessments scheduled at the same time may be initiated prior to the time point. The sequence at a particular time point is:

1. 12-lead ECG.
2. Vital signs (blood pressure and pulse rate).
3. PK blood sample.
4. Safety laboratory assessment blood sample.
5. PK urine sample.

Apart from the predose PK blood sampling, which should occur within 30 minutes prior to investigational product administration, other predose assessments may be performed up to 60 minutes prior to administration of the investigational product.

For occasions when more than one assessment is required at a particular time point, PK blood samples should be prioritised. Additional assessments may be performed if the Principal Investigator considers them necessary for volunteer safety.

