6.3.7 Resting 12-lead electrocardiogram

Twelve-lead ECGs will be recorded at the time points indicated in the study plan ([Table 2](#) and [Table 3](#)).

Electrocardiograms will be recorded in the supine position after the volunteer has rested in this position for at least 10 minutes. A total of 3 12-lead ECG will be recorded at 10 minute intervals at predose and 24-hours postdose.

Only the overall evaluation (normal/abnormal) will be captured in the pCRF. Any abnormalities (including corrected QT interval [QTc] values) should be reviewed by an appropriately qualified person.

The original ECG printouts with variables must be signed and dated and stored in the volunteer’s source workbook as source data.

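### Section 11.1.1 measures early BP and pulse changes against a time-matched Day -1 baseline that is never scheduled, and its fallback passes over the Day 1 predose reading

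*Protocol*

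**What the plan says.** Section 11.1.1 defines change from baseline as the post-treatment value minus baseline, with a baseline for each measure:

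- ECG, blood pressure and pulse: "Time-matched, Day -1 for time points through 24 hours postdose", then "Day 1 predose for all time points after 24 hours postdose".
- Laboratory tests: "Clinical laboratory tests: Day -1".
- Missing baseline: "If a volunteer is missing the baseline collection, the previous nonmissing evaluation will become the baseline value". The next sentence sets the baseline to missing if neither it nor anything preceding it exists, which confirms that the substitution runs backward.

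On what is collected, Section 3.1 has volunteers "admitted to the study centre on Day -1 for assessment of AEs, clinical chemistry, haematology, urinalysis, ECG, and vital signs including weight". Tables 2 and 3 place ECG, BP/pulse and safety laboratory samples at screening and on Day 1 (predose in Table 3), with nothing for them on Day -1. Section 6 states that "other predose assessments may be performed up to 60 minutes prior to administration of the investigational product" (the predose PK blood sample has its own 30-minute limit). Section 6.3.7 adds "A total of 3 12-lead ECG will be recorded at 10 minute intervals at predose and 24-hours postdose", but enters only an overall normal/abnormal evaluation in the case report form.

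Section 12.2.3 commits to summarising continuous safety data as observed values and as change from baseline, and presents ECG results in listings only.

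**The concern.** A time-matched baseline needs a Day -1 profile at the clock times of the postdose assessments. If that profile is not collected, the rule cannot be applied as written and the fallback becomes the working definition for every volunteer. That fallback cannot reach the Day 1 predose value, because it looks back from Day -1.

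At stake are the BP and pulse changes over the first 24 h. This window contains t_max for the oral solution (median 6 h, range 6 to 10 h, Section 1.2). Section 1.4.2 reports raised blood pressure in rat and guinea pig and lower heart rate in guinea pig and dog, so these summaries have some content for the third secondary objective, safety and tolerability.

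**Working it through.** **1. Day -1 assessments, source by source**

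| Source | Labs | ECG | BP/pulse | Matched clock times |
|---|---|---|---|---|
| Section 11.1.1 | assumed | assumed | assumed | assumed (ECG, BP/pulse) |
| Section 3.1 | yes | yes | yes | none given |
| Section 11.2, haematocrit | assumed | not covered | not covered | not applicable |
| Table 2, admission column | blank | blank | blank | none |
| Table 3, Day -1 row | blank | blank | blank | none |

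No source supplies a matched series, whichever of them governs.

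**2. BP/pulse points affected (Table 3)**

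- Through 24 h: 1, 2, 4, 8, 12, 24 h = 6 points.
- Later: Days 7, 14, 21 and discharge on Day 85 = 4 points, already referred to Day 1 predose.
- Without a scheduled baseline: 6 of 10, or 6 x 8 volunteers = 48 values per measure.

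Table 2 also marks vital signs at Visits 3 to 5, which Table 3 does not. Those would fall after 24 h and leave the six unchanged.

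**3. What the fallback selects**

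- If Section 3.1 governs: one admission reading from Day -1, unmatched.
- If the tables govern: screening, Days -28 to -2, so 2 to 28 days before dose.
- Passed over in both cases: the predose reading, at most 60 minutes before dose.

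**4. The switch after 24 h**

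Let b be the fallback baseline, p the predose value, and y(24) and y(D7) the readings at 24 h and Day 7. The difference between the two reported changes is

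[y(D7) - p] - [y(24) - b] = [y(D7) - y(24)] + (b - p).

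The term (b - p) is a difference between two pre-dose readings and says nothing about the drug. Its size cannot be computed from the documents.

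**5. Laboratory tests**

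Table 3 marks 5 postdose laboratory points: Days 7, 14, 21, 28 and 84. If Section 3.1 governs, all 5 have a Day -1 baseline and no fallback is needed. If the tables govern, all 5 fall back to screening although a predose sample is marked. There is no switch of reference and no laboratory point through 24 h.

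Table 6 gives 7 chemistry and 7 haematology samples. This is reproduced in two ways:

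- Table 3 marks: screening, predose, Days 7, 14, 21, 28, 84 = 7.
- Table 3 footnote c: Days 7, 14, 28 and End of Study = 4, plus screening, Day -1 and predose = 7.

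So Table 6 does not settle whether a Day -1 sample is drawn.

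**6. ECG**

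With only normal/abnormal captured and results only listed, the case report form holds no numeric value from which the ECG change promised in Section 11.1.1 could be formed.

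**7. With Day 1 predose as the reference**

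All 10 BP/pulse points in Table 3 have a scheduled baseline at most 60 minutes old, and all 5 laboratory points have a scheduled predose sample.

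**The case against.** The strongest reply is that Section 3.1 does provide for laboratory tests, ECG and vital signs at admission on Day -1, and that Section 11.2 relies on a Day -1 haematocrit. On that reading the laboratory baseline exists, and the BP/pulse fallback is about a day old. The tables are not a clean arbiter either: Table 3 marks safety samples on Day 21, which its own footnote omits. This stands. For laboratory tests the problem is a contradiction between text and tables, not a plain absence.

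A reader might infer that every early change is measured against a value up to 28 days old. The documents support that only if the tables govern, and then only as the upper end of a range starting at 2 days. A reader might also infer lost precision for numeric ECG changes, because the fallback ignores the predose triplicate. The protocol runs no such analysis.

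The results are also descriptive, without hypothesis tests, and observed values are summarised beside the changes. That limits the damage, but it does not make the rule workable: a single admission reading cannot be matched to six clock times.

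**Conclusion.** The point holds for BP and pulse whichever part of the protocol governs: 6 of 10 postdose points in Table 3, or 48 values per measure with 8 volunteers, have no scheduled baseline. The substitute is a poorer reference than the predose reading already collected, and the reference changes after 24 h. For laboratory tests the point is conditional: 5 of 5 postdose points fall back to screening if the tables govern, none if Section 3.1 does. For ECG it is a minor inconsistency, a promised change with no captured number behind it.

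Severity is moderate. The effect is confined to descriptive safety summaries; recovery of radioactivity, the primary endpoint, is untouched. The counts assume that the Table 3 marks are complete and that all 8 volunteers are assessed at each point.

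**What to change.** In Section 11.1.1:

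- Delete the time-matched Day -1 clause. Use Day 1 predose as the BP/pulse baseline at all postdose times, or the last non-missing value before dosing if predose is missing.
- Define the laboratory baseline as the last non-missing value before dosing. This works whether or not a Day -1 sample is drawn.
- Drop the ECG change from baseline, or limit it to a shift in the normal/abnormal evaluation from predose.

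Then reconcile Section 3.1, the haematocrit definition in Section 11.2 and Tables 2 and 3 on whether Day -1 assessments are done.

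The changes to Section 11.1.1 are wording only and use readings already marked in Table 3. Reconciling the schedule needs a decision by the sponsor on which text governs. The statistical cost is that a single predose baseline does not correct for diurnal variation. No matched series is scheduled that could do so, and at 24 h the predose reading is within about an hour of the same clock time. If diurnal correction is wanted, the alternative is to schedule the matched Day -1 readings, which adds assessments.
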